7.3.4 Quantitative Efficacy Variables based on Serum or Urine M-Protein, and/or Serum FLCs

Serum and urine M-protein and serum FLCs were analyzed by a local laboratory at the beginning of the study and by central laboratory for subjects enrolled after Nov 2014 (starting from cohort 7c/ cohort 8 partially) using the response criteria for MM as defined in the current version of the protocol. The following parameters will be measured by visit:

- Serum M-protein level [g/L]
 - Measurements are given g/L, g/dL, mg/L or mg/dL. All values will be converted to [g/L].
- Urine M-protein result [g/24h]
 - Measurements are given g/24h or mg/24h. All values will be converted to [g/24h].
- Lambda FLCs [mg/L]
 - Values smaller than the limit of quantification will be analyzed with the value for the limit of quantification.
- Kappa FLCs [mg/L]
 - Values smaller than the limit of quantification will be analyzed with the value for the limit of quantification.
- Kappa/lambda FLC ratio
 - Kappa/lambda FLC ratio will be recalculated by biostatistics.

For all of these parameters, absolute and percentage changes from baseline will be calculated by visit.

Moreover, the following variables will be derived per subject across timepoints:

Relative change (%) in serum M-protein level from baseline to post-baseline nadir:

This variable will be calculated for all subjects that have measurable serum M-protein levels at baseline and at least 1 post-baseline serum M-protein measurement. The post-baseline nadir will

be the smallest serum M-protein level recorded after baseline. The relative change (%) will be derived as follows:

$100 * (\text{serum M-protein level at post-baseline nadir} - \text{baseline serum M-protein level}) / (\text{baseline serum M-protein level})$.

Relative change (%) in urine M-protein result from baseline to post-baseline nadir:

This variable will be calculated for all subjects that have measurable urine M-protein results at baseline and at least 1 post-baseline urine M-protein measurement. The post-baseline nadir will be the lowest urine M-protein result recorded after baseline. The relative change (%) will be derived as follows:

$100 * (\text{urine M-protein result at post-baseline nadir} - \text{baseline urine M-protein result}) / (\text{baseline urine M-protein result})$.

In case any new anti-MM treatments are given before end of study (see also section 8.3), this will be regarded as protocol non-compliance. M-protein values measured after start of new anti-MM treatment will be flagged in listings. Moreover, these will be excluded from tables and will not be taken into account when deriving relative changes from baseline to post-baseline nadir.

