### Secondary Endpoints

- 1. Pharmacokinetics of MOR03087 +/- LEN or POM
- 2. Absolute and percent change from baseline in measurements of B, T, and NK cell populations
- 3. Overall response rate (stringent complete response [sCR], complete response [CR], very good partial response [VGPR], partial response [PR]), further tumor response rates (CR, stringent complete response [sCR], PR, minimal response [MR], VGPR), and SD rate
- 4. Duration of response, time to progression (TTP), and PFS
- 5. Absolute and percentage change from baseline in serum and urine M-protein levels
- 6. Absolute and percent change from baseline in serum FLC levels and serum FLC ratio
- 7. Absolute changes from baseline in laboratory parameters (serum chemistry, hematology, urinalysis) and clinically relevant abnormal values
- 8. Absolute change from baseline in overall quality of life scores
- 9. Change in cytokines from baseline

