# **18.3 Response Criteria for Multiple Myeloma**

The tumor response criteria for multiple myeloma in this study are those defined in Table 14 below. All of them are based on the International Myeloma Working Group Uniform Response Criteria (Durie 2006), except for MR, which is based on the adopted EBMT criteria (Blade 1998).

Response	Criteria ^a
subcategory	
sCR	CR as defined below plus     Normal FLC ratio and     Absence of clonal cells in bone marrow ^b by immunohistochemistry or     immunofluorescence ^c
CR	
 
Negative immunofixation on the serum and urine and
 
Disappearance of any soft tissue plasmacytomas and
 
< 5% plasma cells in bone marrow^b
 

VGPR	
 
Serum and urine M-protein detectable by immunofixation but not electrophoresis or
 
≥ 90% reduction in serum M-protein plus urine M-protein level < 100 mg/24 hours
 

PR	
 
≥ 50% reduction of serum M-protein and reduction in 24-hour urinary M-protein by ≥ 90% or to < 200 mg/24 hours
 
If the serum and urine M-protein are unmeasurable, a ≥ 50% decrease in the difference between levels of involved and uninvolved free-light-chains instead of the M-protein criteria
 
In addition to the above-listed criteria, if present at baseline, a ≥ 50% reduction in the size of soft tissue plasmacytomas is also required
 

MR ^{d,e}	
 
25-49% reduction in level of serum M-protein
 
50-89% reduction in 24-hour urinary M-protein, which still exceeds 200 mg/24 hours If present at baseline, 25-49% reduction in the size of soft tissue plasmacytomas (by radiography or clinical examination)
 
No increase in the size or number of lytic bone lesions (development of a compression fracture does not exclude response)
 

$\mathbf{SD}^{\mathrm{f}}$	• Not meeting criteria for CR, VGPR, PR, MR, or PD

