2.2.2 Secondary Endpoints

Secondary endpoints are

1. Pharmacokinetics of MOR03087 +/- LEN or POM
2. Absolute and percent change from baseline in measurements of B, T, and natural killer (NK) cell populations
3. Overall response rate (stringent complete response [sCR], complete response [CR], very good partial response [VGPR], partial response [PR]), further tumor response rates (CR, sCR, PR, minimal response [MR], VGPR), and stable disease (SD) rate
4. Duration of response (DoR), time to progression (TTP), and progression-free survival (PFS)
5. Absolute and percent change from baseline in serum and urine M-protein levels
6. Absolute and percent change from baseline in serum free light chain (FLC) levels and serum FLC ratio
7. Absolute changes from baseline in laboratory parameters (serum chemistry, haematology, urinalysis) and clinically relevant abnormal values
8. Absolute change from baseline in overall quality of life scores
9. Change in cytokines from baseline

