7.2 Structure of Tables

Three different types of tables will be produced:

- 1) tables for the total study data by cohort
- 2) tables for the total study data by part
 - bi-weekly (Part A)
 - weekly without dexamethasone (Part B)
 - weekly with dexamethasone (Part C)
 - combination with POM (Part D)
 - combination with LEN (Part E)
- 3) tables for recommended dose data by part
 - weekly with dexamethasone (Part C)
 - combination with POM (Part D)
 - combination with LEN (Part E)

The safety and baseline summary tables will additionally contain a summary of the total number of subjects of the corresponding analysis (sub-) group.

In the tables for recommended dose data, all data from the recommended (or MTD) dose levels will be summarized together, i.e. data from the confirmation cohort will be combined with the data from the cohort of the dose escalation scheme that received the same dose and regimen and combination treatment (if applicable).

Summaries of type 2) and 3) will be referred to as combined presentations or combined data in subsequent sections, in contrast to summaries by dose level.

The 95% confidence intervals will only be presented for these combined presentations and will not be presented by dose level due to the small number of subjects by dose level.

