9.3.1 Pharmacodynamic Parameters Measured in Blood or Urine

Actual values and absolute and percent changes from baseline will be summarised descriptively by visit for the pharmacodynamic parameters specified below. Moreover, 95%-confidence intervals will be provided for mean and median changes in summaries of absolute changes from baseline and for median changes in summaries of percentage changes from baseline in all combined presentations.

Measurements of B, T, and NK cell populations and CD16 expression on NK cells: Descriptive summaries (as specified above) will be provided for the following parameters:

- Measurements of B, T, and NK cells [%]
Measurements of B, T, and NK cells [/ μ l]

Measurements of B, T, NK cells are given in % and/or as absolute count [/ μ l] by the investigator, whereas the absolute count is often missing. Therefore absolute count [/ μ l] will be also be derived using the lymphocytes absolute values [G/l = $n \cdot 1000 / \mu$ l = /nl] from the laboratory hematology data (lymphocytes absolute * [measurement in % /100]

* 1000, rounded without decimals). Two tables each will be presented, one table based on % values (original values only) and a further table based on absolute counts [μl] (derived and original values, both rounded without decimals).

- CD16 expression on NK cells [Antibodies bound per cell]

The analysis will be based on the unit “antibodies bound per cell”. Measurements cannot be included in the analysis if measurements in the unit “antibodies bound per cell” are missing.

Result of Flow Cytometry of Peripheral MM Cells: Descriptive summaries will be provided for the following parameters:

- Measurements of CD138 cells [Count per 10^6 cells]
- Percentage of malignant CD38 cells [%]
- Measurement of CD38 expression on malignant cells in [MFI] (MFI = Median Fluorescence Intensity)
- Measurement of CD38 expression on malignant cells in [Antibodies bound per cell]

In the summaries of actual values for CD38 variables, only subjects who have counts of CD138+ cells equal and above 100 counts per 10^6 cells at the corresponding visit will be included since for subjects who have counts of CD138+ cells below 100 counts per 10^6 cells no values for CD38 variables will be available. In the summary of absolute and percentage changes from baseline for CD38 variables, only subjects who have counts of CD138+ cells above 100 counts per 10^6 cells at both baseline and post-baseline visits will be included.

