Serum and Urine M-Protein, Serum FLCs: Serum and urine M-protein and serum FLCs were analyzed by a local laboratory at the beginning of the study and by central laboratory enrolled after November 2014 (starting from cohort 7c/ cohort 8 partially, see section 7.3.4 for parameters measured and derived). Descriptive summaries by visit (including summaries of absolute and percentage changes) will be provided for the following parameters by visit:

- Serum M-protein level [g/L]
- Urine M-protein result [g/24h]
- Lambda FLCs [mg/L]
- Kappa FLCs [mg/L]
- Kappa/lambda FLC ratio

Moreover, descriptive summaries across time points will be prepared for

- relative change (%) in serum M-protein result from baseline to post-baseline nadir
- relative change (%) in urine M-protein result from baseline to post-baseline nadir.

Anti-TT data (Anti-Tetanus Toxoid IgG data): Anti-TT data will only be presented in listings.

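### Change in the kappa/lambda FLC ratio is pooled across kappa and lambda disease, where improvement moves it in opposite directions, so in mixed groups the summary reflects clone mix as well as drug effect

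*SAP*

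**What the plan says.** Secondary endpoint 6 in protocol section 11 is "Absolute and percent change from baseline in serum FLC levels and serum FLC ratio", and SAP 2.2.2 repeats it.

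SAP 7.3.4 lists lambda FLC, kappa FLC and their ratio as by-visit parameters. The ratio has one fixed orientation: "Kappa/lambda FLC ratio will be recalculated by biostatistics". On change, the section says: "For all of these parameters, absolute and percentage changes from baseline will be calculated by visit".

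SAP 9.3.1 then says: "Descriptive summaries by visit (including summaries of absolute and percentage changes) will be provided for the following parameters by visit". It adds 95% intervals for mean and median absolute change and, for percentage change, only "for median changes in summaries of percentage changes from baseline in all combined presentations". SAP 7.2 groups tables by cohort, by part, and by part at the recommended dose, and restricts intervals to the last two. The subgroups in SAP 7.4 do not include light-chain type, and SAP 9.2.1 applies them only to BOR, ORR, CBR, DCR and PFS.

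Protocol Table 14 (section 18.3) orients FLC by clone. Stringent CR needs a normal ratio. Where M-protein is unmeasurable, PR is judged on the "difference between levels of involved and uninvolved free-light-chains instead of the M-protein criteria", and PD uses the same difference.

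**The concern.** The kappa/lambda ratio has no common direction of benefit. In a kappa clone the tumour chain is the numerator, so the ratio starts high and falls with response. In a lambda clone it is the denominator, so the ratio starts near zero and rises. Kappa FLC is likewise the tumour marker in one subject and the uninvolved chain in the next.

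Elsewhere the SAP does attend to direction: section 7.3.5 gives the quality-of-life functional and symptom scales separate formulas and says which way each improves. FLC has no such rule.

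At stake is the readability of the ratio half of a named secondary endpoint. Under SAP 4.3 the same tables would be re-run in the follow-up analyses.

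**Working it through.** The documents state no FLC effect size, FLC values or kappa share, so there is no planned figure to reproduce. All FLC values below are assumptions.

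**1. Ratio, involved chain halved in everyone.** Assume involved 500 mg/L and uninvolved 10 mg/L, with the uninvolved chain unchanged.
- Kappa subject: 500/10 = 50 to 250/10 = 25, a change of -25 or -50%.
- Lambda subject: 10/500 = 0.02 to 10/250 = 0.04, a change of +0.02 or +100%.
- Mean percentage change with kappa share p is p × (-50) + (1 - p) × 100: +25% at p = 0.5, about 0% at two thirds, -20% at 0.8.
- Mean absolute change at the same shares: -12.5, -16.7 and -20.0. Lambda subjects barely register.

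**2. Ratio, involved chain 50% higher in everyone.** Kappa +50%. Lambda 0.02 to 10/750 = 0.0133, or -33.3%. At p = 0.5 the mean is (50 - 33.3)/2 = +8.3%. In such a group, uniform improvement (+25%) and uniform worsening (+8.3%) both give a positive mean.

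**3. Extreme case: all nine subjects normalise.** Nine is the minimum recommended-dose group in SAP section 5.
- Kappa: (1 - 50)/50 = -98%. Lambda: (1 - 0.02)/0.02 = +4900%.
- Median percentage change: -98% with 5 kappa and 4 lambda; +4900% with 4 kappa and 5 lambda.
- Mean percentage change with 6 kappa and 3 lambda: (6 × (-98) + 3 × 4900)/9 = +1568%. Mean absolute change for the same subjects: (6 × (-49) + 3 × 0.98)/9 = -32.3. The two summaries disagree in sign.
- Interval for the median: SAP 7.1 specifies a nonparametric interval. If it is the usual order-statistic interval, at n = 9 it runs from the 2nd to the 8th ordered value (coverage 1 - 2 × (1 + 9)/512 = 96.1%). With at least two subjects of each type it would run from -98% to +4900%, although every subject had the same response.

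**4. Less extreme groups of nine.** In a simulation with lognormal values and a mean involved-chain change of -52%, the mean percentage ratio change was above zero in 95%, 80% and 52% of groups with 5, 6 and 7 kappa subjects. The typical group median was -20%, -40% and -50%.

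**5. Single chains.** In the setting of step 1, with two thirds kappa subjects, mean change is -33% for kappa and -17% for lambda, against -50% in the involved chain. The effect is diluted, not reversed. Opposite movement needs recovery of the uninvolved chain: if it rises from 10 to 15 while the involved chain falls 90%, the two chains change by +50% and -90%.

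**6. How often groups are mixed.** The probability is 1 - p^n - (1 - p)^n. For p from 0.50 to 0.75 this is 56-75% at n = 3, 82-97% at n = 6 and 93-99.6% at n = 9.

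**7. Involved orientation.** In step 1 every subject has involved FLC -50% and involved minus uninvolved (250 - 10)/(500 - 10) - 1 = -51%. With a 90% fall, the figures are -90% and (50 - 10)/490 - 1 = -92%. The clone mix no longer matters.

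**The case against.** A reader might infer that endpoint 6 as a whole cannot be read. The documents do not support that. Opposite movement is certain only for the ratio. Single-chain summaries are mainly diluted, the mean absolute ratio change keeps the kappa subjects' sign, and SAP 7.1 lists individual values. The pooling is also within cohort, part or recommended-dose group, not over the whole study.

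A reader might also infer that the SAP contradicts Table 14, or that efficacy results are affected. Neither follows. The SAP carries out the endpoint as the protocol words it, so the gap lies in the endpoint definition too. Under SAP 7.3.3 the investigator assesses response by the protocol criteria. Table 14 uses the FLC difference only where M-protein is unmeasurable, while entry requires serum or urine M-protein above a threshold. Progression in a lambda subject is still captured as PD.

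The full-normalisation example is extreme, and in the simulation group medians stayed negative when kappa subjects were the majority. SAP 9.3.1 attaches no interval to mean percentage change, although protocol 15.5 does plan one at the recommended dose. Section 13 of the SAP, the table list, is redacted, so a split there cannot be ruled out.

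All of this narrows the point. It does not give the pooled ratio change a common direction.

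**Conclusion.** The point holds for the kappa/lambda ratio. As sections 7.3.4 and 9.3.1 read, the pooled ratio change in a mixed group reflects the kappa:lambda mix as well as drug effect. This is worst for mean and median percentage change and for the interval around the median. Mean absolute change is dominated by kappa subjects, and single-chain summaries are weakened by mixing tumour and uninvolved chains.

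The direction of the problem follows from how the ratio is built; its size rests on assumed FLC values and kappa shares. It concerns one descriptive secondary endpoint, with no stated role in the MTD, DLTs or dose escalation. Response rates, TTP, PFS and M-protein summaries stand.

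**What to change.** In SAP 7.3.4, define the involved chain per subject:
- from the documented immunoglobulin/light-chain type (protocol 11.4.2 records immunoglobulin type but does not say whether the light chain is included);
- if the light chain is not recorded, from whether the baseline kappa/lambda ratio lies above or below the laboratory reference range;
- subjects with no recorded type and a normal baseline ratio are left out of these summaries and listed.

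In SAP 9.3.1, add by-visit summaries of change in involved FLC, involved minus uninvolved FLC, and the involved/uninvolved ratio (median or log scale). Keep the kappa, lambda and kappa/lambda change tables, since the protocol names FLC levels and ratio, but show them split by involved chain rather than pooled.

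No new data are needed. The cost is a small derivation, a few more tables, and smaller groups in the split tables.

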3.2 Selection of Study Population

This is a phase I/IIa study in adult subjects with relapsed or refractory MM as monotherapy and in combination with standard therapy. Key inclusion criteria identified in the protocol are

1. Male or female subjects ≥ 18 years of age
2. Presence of serum M-protein ≥ 0.5 g per 100 mL (≥ 5 g/L) and/or urine M-protein ≥ 200 mg per 24-hour period
3. Life expectancy of > 3 months
4. Karnofsky performance status $\geq 60\%$
5. Absolute neutrophil count ≥ 1.0 (1,000/mm³)
6. Total bilirubin $\leq 2 \times$ the upper limit of normal (ULN)
7. Alanine transaminase and aspartate aminotransferase $\leq 2.5 \times$ ULN
8. Hemoglobin ≥ 8 g/dL

Additional key inclusion criteria are defined differently for monotherapy and different combination therapies:

Additional Key Inclusion Criteria for Treatment With MOR03087 With/Without Dexamethasone

1. Documented diagnosis of MM; specifically, relapsed or refractory MM defined as:
 - Failure of at least 2 previous therapies; previous therapies must include an immunomodulatory agent and a proteasome inhibitor (either together or as part of different therapies)
 - All subjects must have documented progression during or after their last prior therapy for MM
2. Creatinine clearance ≥ 30 mL/min (calculated using the Cockcroft-Gault equation)
3. Platelets:
 - $\geq 80 \times 10^9/L$, without previous transfusion within the last 4 weeks before first study drug administration

- $\geq 50 \times 10^9/L$ (for dose levels ≥ 4 mg/kg with or without DEX). Subjects are not allowed to have received platelet transfusion within the last 4 weeks before study drug administration.

Additional Key Inclusion Criteria for the Treatment With MOR03087, Dexamethasone and Lenalidomide

1. Documented diagnosis of MM; specifically, relapsed or refractory MM defined as:
 - Received at least 1 previous therapy
 - All subjects must have documented progression during or after their last prior therapy for MM
2. Creatinine clearance ≥ 50 mL/min (calculated using the Cockcroft-Gault equation)
3. Platelets:
 - $\geq 75 \times 10^9/L$ for subjects in whom $< 50\%$ of bone marrow nucleated cells are plasma cells
 - $\geq 30 \times 10^9/L$ for subjects in whom $\geq 50\%$ of bone marrow nucleated cells are plasma cells.

Additional Key Inclusion Criteria for the Treatment With MOR03087, Dexamethasone and Pomalidomide

1. Documented diagnosis of MM; specifically, relapsed and refractory MM defined as:

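### By-visit changes in serum and urine M-protein lack the baseline-measurability condition the SAP gives its nadir variables, so subjects without M-protein in that fluid can dilute the mean and hold the median at zero

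*SAP*

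**What the plan says.** Change from baseline in serum and urine M-protein is secondary endpoint 5 (SAP 2.2.2).

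- **By-visit changes.** SAP 7.3.4 lists five parameters (serum M-protein, urine M-protein, lambda and kappa free light chains, and their ratio) and continues: "For all of these parameters, absolute and percentage changes from baseline will be calculated by visit". SAP 9.3.1 puts them into tables: "Descriptive summaries by visit (including summaries of absolute and percentage changes) will be provided for the following parameters by visit". Neither place names a subset.
- **Statistics.** SAP 9.3.1 plans intervals in the combined presentations. For absolute change, "95%-confidence intervals will be provided for mean and median changes in summaries of absolute changes from baseline". For percent change there is an interval only "for median changes in summaries of percentage changes from baseline in all combined presentations".
- **Nadir changes.** SAP 7.3.4 does set a condition here. For serum: "This variable will be calculated for all subjects that have measurable serum M-protein levels at baseline". For urine: "This variable will be calculated for all subjects that have measurable urine M-protein results at baseline".
- **Entry.** SAP 3.2, like Protocol 8.1, requires "Presence of serum M-protein ≥ 0.5 g per 100 mL (≥ 5 g/L) and/or urine M-protein ≥ 200 mg per 24-hour period". One fluid is enough.
- **Low values.** SAP 7.3.4 has a substitution rule, "Values smaller than the limit of quantification will be analyzed with the value for the limit of quantification", but gives it under lambda and kappa free light chains only. No such rule is readable for M-protein.
- **Exclusions.** The only M-protein values that SAP 7.3.4 removes from tables are those taken after a new anti-myeloma treatment starts. Neither the Safety nor the Efficacy Evaluable Population (SAP 6) requires measurable M-protein in the fluid being analysed.

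**The concern.** A subject who entered on serum M-protein alone has nothing in urine that the drug could lower, and the reverse holds for a subject who entered on urine alone. If that subject sits in the by-visit table with 0 at baseline and 0 at the visit, the change is 0 whatever the treatment does. The table then reflects two things at once: the fall in subjects who can fall, and the proportion of subjects who secrete in that fluid. Two dose groups or parts with the same drug effect but a different mix would show different means, and possibly different medians.

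The SAP accepts the principle elsewhere. It conditions the nadir variables on baseline measurability, and in 9.3.1 it limits changes in the CD38 variables to subjects with enough CD138+ cells at both visits. The by-visit M-protein changes are the exception. Because measurement moved from local to central laboratories during the study (SAP 7.3.4), an unstated coding of undetectable values might also differ between early and late cohorts.

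**Working it through.** **Inputs.** A recommended-dose group has at least 9 subjects (SAP 5). Cohorts have 3 or 6. Parts D and E have up to 18 subjects and Part C up to 24 (Protocol synopsis). The entry level for urine is 200 mg/24h, that is 0.2 g/24h. The share *q* of subjects with no M-protein in a given fluid is not in the documents, so I assume values from 0.2 to 0.7. The urine baseline of 1.0 g/24h is also assumed. The plan states no figure for the M-protein analysis. Its only figure for a group of 9 is the adverse-event detection probability in Protocol 15.9, which reproduces: 1 - 0.83^9 = 0.813 (stated 81%) and 1 - 0.77^9 = 0.905 (stated 90%). It is not in dispute and serves only to fix the group size.

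**Step 1: absolute change, undetectable recorded as 0.** If *k* of *n* subjects are at 0 at both times, the mean over all subjects is (n - k)/n times the mean in the measurable subjects. The median is exactly 0 when k > n/2. Take n = 9, k = 5, and four subjects starting at 1.0 g/24h:

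| Fall in the four | Median, all 9 | Mean, all 9 | Median and mean, the 4 measurable |
|---|---|---|---|
| 0% | 0 | 0 | 0 |
| 50% | 0 | -0.222 | -0.5 |
| 90% | 0 | -0.400 | -0.9 |
| 100% | 0 | -0.444 | -1.0 |

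With n = 12 and k = 7, where the five measurable subjects all clear 1.0 g/24h, the median is 0 and the mean is -5/12 = -0.417. The interval for the median from order statistics 3 and 10 has coverage 1 - 2(1 + 12 + 66)/4096 = 96.1% and runs from -1.0 to 0. The same algebra holds for serum.

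**Step 2: how often the median would be 0.** Suppose every measurable subject falls and subjects are independent. The probability of a zero median is P(X ≥ floor(n/2) + 1) with X ~ Binomial(n, q):

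| n | q = 0.2 | 0.3 | 0.4 | 0.5 | 0.6 | 0.7 |
|---|---|---|---|---|---|---|
| 3 | 0.10 | 0.22 | 0.35 | 0.50 | 0.65 | 0.78 |
| 6 | 0.02 | 0.07 | 0.18 | 0.34 | 0.54 | 0.74 |
| 9 | 0.02 | 0.10 | 0.27 | 0.50 | 0.73 | 0.90 |
| 18 | 0.00 | 0.02 | 0.14 | 0.41 | 0.74 | 0.94 |
| 24 | 0.00 | 0.01 | 0.11 | 0.42 | 0.79 | 0.97 |

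A zero median is unlikely at small shares and likely at large ones. Dilution of the mean, by the factor 1 - q on average, occurs at any non-zero share.

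**Step 3: percent change.** With a baseline of 0 the ratio does not exist, so the subject contributes no value. Trace baselines do contribute: 0.01 to 0.05 g/24h is +400%, 0.02 to 0.06 is +200%, and 0.05 to 0.10 is +100%, whereas 0.20 to 0.25 is +25%. Four subjects at -50% together with the three trace subjects give a mean of (4 × -50 + 400 + 200 + 100)/7 = +71% and a median of -50%. The mean is badly distorted. The median, which carries the interval, is not moved in this example.

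**The case against.** The strongest reply is that inclusion is inferred. Non-measurable subjects enter the absolute change only if an undetectable result is stored as 0. If it is stored as missing, they drop out, because SAP 7.1 summarises non-missing values and imputes nothing. Parts of the SAP also cannot be read: the reporting conventions in section 11 are listed in the contents but are not in the available text, the planned table list is redacted, and there are redactions inside 7.1. A coding rule or table subset could sit there. This stands, and it makes the dilution conditional. It does not remove the difference, visible within 7.3.4, between the nadir variables and the by-visit changes.

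On size, the reply is that a zero median needs more than half the group to be non-measurable in that fluid, and nothing in the documents says how large that group is. At a 20% share the chance is 0.02 for n = 9. This also stands.

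On consequence, the endpoint is descriptive and secondary in a non-randomized study, and the nadir summaries already give the restricted picture for both fluids. Both points are correct and limit the importance of the gap.

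On remedy, a filter has a price. A subject with no urine M-protein at baseline who later develops it would leave the tables, although a rise in urine M-protein can define progression (Protocol 18.3). That is a fair objection, and the fix has to deal with it.

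**Conclusion.** The by-visit M-protein summaries should carry the same baseline condition as the nadir variables. Followed as written, and if undetectable values are recorded as 0, the mean absolute change is multiplied by the measurable fraction of the group (4/9 in the example). The median is 0 once non-measurable subjects exceed half (5 of 9, or 7 of 12). These results rest on the assumed coding and on an assumed share.

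Four stronger readings are not supported:

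- A reader might infer that the median *will* be zero, or that non-measurable subjects are certainly in the tables. The documents give neither the share nor the coding.
- A reader might infer that the percent-change analysis is invalid. Zero baselines simply give no value, and the SAP plans no interval for the mean percent change, which is the statistic that trace baselines distort most.
- A reader might infer that the by-visit tables contradict the nadir analysis. They are different variables in different sets of subjects, and the nadir analysis itself is sound on this point.
- A reader might want the entry thresholds imposed on the nadir variables. No defect in those variables has been shown. Since SAP 7.1 takes baseline from Cycle 1 Day 1 when available, a subject eligible at screening could fall below a threshold by then and be lost.

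Response rates and PFS rest on investigator assessment, and dose decisions on toxicity, so none of them is affected. What is at stake is the interpretation of one descriptive secondary endpoint. The change is cheap enough to be worth making.

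**What to change.** In SAP 7.3.4 and 9.3.1:

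1. Restrict the by-visit absolute and percent changes in serum and in urine M-protein, and their confidence intervals, to subjects with measurable M-protein in that fluid at baseline. Use the same definition of measurable as the nadir variables, and write that definition down once.
2. State how an undetectable M-protein result is coded, for local and central laboratory values alike.
3. Print in each table the number of subjects contributing.
4. List the remaining subjects' values by visit, so that new or rising M-protein in them stays visible.

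The cost is a few sentences and a program filter. The tables will have a smaller n, and emergent M-protein in subjects not measurable at baseline will appear only in listings. The SAP should say so.
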